8.3.3. REVOLADE Exposure during Observational Period

- REVOLADE exposure
 - Start date
 - o Stop date if recorded
 - Hospital discharge date (if hospitalized)
 - o Doses administered (including all changes in dose)
- Indication for REVOLADE
- If REVOLADE discontinued, date and reason for discontinuation

8.3.4. On label and off label definitions

If information on splenectomy, prior medication use, and contraindications for surgery is available, then use of eltrombopag for a patient will be categorized into the following groups:

- On-label use:
 - patient is an adult, has a diagnosis of chronic ITP, has been splenectomized or has a contraindication for surgery, and has received prior corticosteroids, immunoglobulins therapy; or
 - o patient is an adult, has a diagnosis of chronic HCV, has clinically meaningful thrombocytopenia limiting interferon-based therapy, and date of eltrombopag is after REVOLADE approval date (September 2013).
- Off-label use:
 - o patient is an adult, has chronic ITP, but has not received prior corticosteroids, immunoglobulins therapy or has not been splenectomized and does not have a contraindication for surgery;
 - o patient is an adult, has HCV, but does not have clinically meaningful thrombocytopenia limiting interferon-based therapy or the date of REVOLADE is prior to REVOLADE approval date;
 - o patient is an adult, but does not have ITP or HCV;
 - o patient is < 18 years of age

If there is no information on splenectomy, prior medication use, and contraindications for surgery, then classification will be more general:

- On-label use:
 - o patient is an adult and has a diagnosis of chronic ITP; or
 - o patient is an adult and has a diagnosis of HCV with clinically meaningful thrombocytopenia limiting interferon-based therapy, and date of eltrombopag after REVOLADE approval date
- Off-label use:
 - o patient is an adult, but has acute rather than chronic ITP;

- o patient is an adult, but does not have ITP and does not have HCV with clinically meaningful thrombocytopenia or has clinically meaningful thrombocytopenia limiting interferon-based therapy but date of eltrombopag is prior to REVOLADE approval date;
- o patient is an adult, but does not have ITP or HCV; or
- o patient is < 18 years of age

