REVOLADE received marketing authorization from the European Medicines Agency (EMA) in March 2010 for the treatment of adult splenectomised chronic ITP patients who are refractory to other treatments (e.g., corticosteroids, immunoglobulins). As part of the indication, REVOLADE may also be considered as second line treatment for adult non-splenectomised patients where surgery is contraindicated.

The efficacy and safety of REVOLADE in adult patients with chronic ITP were evaluated in three randomized, double-blind, placebo-controlled trials and in an open-label extension trial. Trial 1 randomized 114 patients (2:1) to REVOLADE 50 mg or placebo. Trial 2 randomized 117 patients (1:1:1:1) among placebo or one of three dose regimens of REVOLADE, 30 mg, 50 mg, or 75 mg each administered daily. In the third trial, 197 patients were randomized (2:1) to receive either REVOLADE 50 mg once daily

(n = 135) or placebo (n = 62) for 6 months, during which time the dose of REVOLADE could be adjusted based on individual platelet counts. Patients were allowed to taper or discontinue concomitant ITP medications after being treated with REVOLADE for 6 weeks. Overall, during clinical development for the ITP indication, REVOLADE showed a dose-dependent increase in platelet counts and a decrease in bleeding events compared with placebo, and was generally safe and well tolerated.

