8. RESEARCH METHODS

8.1. Study Design

This is a multi-national, multi-center study involving the retrospective review of approximately 300 to 450 patient medical records from selected European countries including France, Germany, Spain, and other relevant selected European Union (EU) Member States (see Section 8.2) with each country contributing approximately six or seven sites. It is estimated that 18 to 21 hospital or office based sites overall where prescribers of REVOLADE have been identified and medication records exist, will be targeted for recruitment. The investigators will be queried to identify REVOLADE treated patients during the periods of interest. To the extent possible, a selection of sites representative of the country prescription volumes will be enroled.

Medical records of all consecutive patients treated with REVOLADE, irrespective of indication, dose, treatment duration or any patient characteristic will be retrospectively reviewed to confirm eligibility.

Medical records will be reviewed for data from REVOLADE first prescription. This study involves no intervention, and will not impact the usual medical care or affect the treatment of patients. Thus, the study will reflect a real world medical practice without the potential for prescriber response bias, which may occur in prospective studies (i.e., the Hawthorne Effect) (Mangione-Smith, 2002).

The study overview is provided in the figure below:

[figure not shown]

Figure 1 REVIEU Study Overview

In Figure 1 EU approval for first indication (March 2010) refers to the approval of REVOLADE: "Revolade is indicated for adult chronic immune (idiopathic) thrombocytopenic purpura (ITP) splenectomised patients who are refractory to other treatments (e.g. corticosteroids, immunoglobulins). Revolade may be considered as

Page 116 WEUKBRE7133

second line treatment for adult non-splenectomised patients where surgery is contraindicated."

EU approval for second indication refers to "Revolade is indicated in adult patients with chronic HCV infection for the treatment of thrombocytopenia, where the degree of thrombocytopenia is the main factor preventing the initiation or limiting the ability to maintain optimal interferon-based therapy."

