8.2.4. Site Selection

The study will be implemented at approximately 18- 21 sites in selected countries in the EU (six or seven sites per country) by selecting sites that are geographically dispersed to best represent different practices across regions/provinces within the selected EU Member States. Also, selection of study sites will be determined at the country level in order to obtain a representative sample of sites reflective of the treatment patterns within each country. Site qualification and selection criteria will include: type of physician/hospital, geographic location (e.g., rural, urban), practice setting (clinics, academic setting, and reference centre), capture area, estimated eligible patient availability, number of patients seen in previous year, availability and number of eltrombopag pharmacy records), and staffing availability.

The Study will target a representative sample of physicians who prescribe REVOLADE, irrespective of the indication. These include hematologists, oncologists, virologists, hepatologists, internal medicine and other specialists from the hospital or office based setting. The data collected in the Study will be used to determine the characteristics of patients for whom REVOLADE is prescribed and to understand if it is being prescribed in accordance with the product labelling.

The site and investigator identification, selection and recruitment process will be detailed in the Site Recruitment Plan document, which will be developed at study start-up. This document will describe the process for site identification, site recruitment process with flow chart, site qualification process via the study specific site qualification questionnaire. In addition, this document will describe the process how to contact and conduct follow-up activities of identified sites and investigators. Potential risks to the plan will be identified early in its development to ensure that proper risk mitigation measures are put in place to ensure achievement of site enrolment objectives.

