8.3.2. REVOLADE General Information

The following data will be collected for all patients enrolled:

WEUKBRE7133

Page 120

• Date of informed consent.

The following data will be collected from the medical records for all patients enroled:

- Demographics:
 - o age at time of first REVOLADE prescribing dose
 - o gender
 - o race/ethnicity (where allowed by local regulation)
- Diagnosis of chronic ITP and date (if medical record data available, will record the disease phase as 'acute' or 'chronic' ITP specifically or just 'ITP', duration of ITP if available)
- Diagnosis of HCV and date; information on previous treatment with antiviral therapy
- Diagnosis of other conditions and date
 - o Hematologic malignancies (AML, MDS, other leukemia, lymphoma, etc)
 - o Aplastic anemia and bone marrow failure
 - o Other
- Medical history for applicable conditions and current medical conditions
 - Surgery (i.e., splenectomized or not)
 - Comorbidities that may be contraindications for surgery (anemia, hyperbilirubinemia, neutropenia, leukopenia, pancytopenia, pneumonia, and others)
 - o Pregnancy status
 - o Non haematological malignancy and type
 - o Comorbidities:
 - Cardiovascular diseases
 - Pulmonary Arterial Hypertension
 - Hypertension
 - Diabetes
- Treatment(s) preceding REVOLADE prescription:
 - Type (corticosteroids, immunoglobulins, cytokines, ribavirin, peginterferon, etc.)
 - Date of treatment initiation
 - Dose and duration
- Concomitant treatment(s) initiated with REVOLADE:
 - Type (corticosteroids, immunoglobulins, cytokines, ribavirin, peginterferon, etc.)
 - o Date of treatment initiation
 - Dose and duration
- All platelet counts (x10⁹/L) at the time of primary medical condition, at initiation of REVOLADE, and dates, and resulting in dose change, by dose

Page 121 WEUKBRE7133

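### Section 8.3.4 classifies ITP use by receipt of two named drug classes, while the label quoted in Section 8.1 asks for refractoriness or second-line use, so the off-label proportion is open to misclassification in both directions

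*Protocol*

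**What the plan says.** Section 8.1 of the Protocol reproduces the indication, which has two ITP arms. The first covers adult chronic ITP in "splenectomised patients who are refractory to other treatments (e.g. corticosteroids, immunoglobulins"; the two drug classes stand there as examples. The second is given again in Section 6.1: "REVOLADE may also be considered as second line treatment for adult non-splenectomised patients where surgery is contraindicated".

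Where information on splenectomy, prior medication and surgical contraindication is available, Section 8.3.4 applies one prior-treatment test to both arms. The patient is on-label if, besides the surgical condition, the patient "has received prior corticosteroids, immunoglobulins therapy". The matching off-label bullet covers an adult with chronic ITP who "has not received prior corticosteroids, immunoglobulins therapy or has not been splenectomized and does not have a contraindication for surgery".

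For treatments before REVOLADE, Section 8.3.2 collects "Type (corticosteroids, immunoglobulins, cytokines, ribavirin, peginterferon, etc", the date of initiation, and "Dose and duration". No response or failure item is listed.

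Section 8.2.4 says the data will be used "to understand if it is being prescribed in accordance with the product labelling". Section 8.5.1 sizes the study on the precision of the off-label proportion.

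**The concern.** The classification is meant to measure agreement with the label, yet its prior-treatment test departs from the label in two ways and is unclear in a third.

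- **Refractoriness is dropped.** A splenectomised patient who had the named drugs and responded is outside the first label arm as quoted but is counted on-label. This lowers the off-label proportion.
- **The example list becomes a closed list.** A patient in either arm whose earlier treatment was of another class can meet the label but is counted off-label. This raises the off-label proportion.
- **The comma has no operator.** A patient given only one of the two classes is on-label under 'or' and off-label under 'and'. The negated bullet does not settle which is meant.

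At stake is the proportion on which the study is sized. Its confidence interval covers sampling error only and would not show an error of this kind.

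**Working it through.** **1. Label and rule side by side (detailed tier of Section 8.3.4)**

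| Patient (adult, chronic ITP) | Label as quoted in 8.1 | Rule in 8.3.4 |
|---|---|---|
| Splenectomised, had both classes, not refractory | outside | on-label |
| Splenectomised, refractory to another class only | inside | off-label |
| Not splenectomised, surgery contraindicated, earlier treatment of another class only | inside (second line) | off-label |
| Surgical condition met, prior treatment condition of the label met, only one of the two classes given | inside | depends on the comma |
| Not splenectomised, surgery contraindicated, had both classes | inside | on-label (agrees) |

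The refractoriness error is confined to the splenectomised arm. The closed-list error reaches both arms.

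**2. The plan's own precision**

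Inputs from Section 8.5.1: n = 400, p = 0.05, 95% level.

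Half-width = 1.96 × √(p(1 − p)/n) = 1.96 × √(0.05 × 0.95/400) = 0.0214, giving 2.9% to 7.1%. This reproduces the stated 2.1 points.

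**3. Misclassification needed to match that precision**

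Let T be the true off-label share, *a* the share of truly on-label patients called off-label, and *b* the share of truly off-label patients called on-label. Then

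observed = T(1 − b) + (1 − T)a.

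The documents give no value for *a* or *b*, so the values below are assumptions shown as a range, with T = 5%.

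| a | b | Observed off-label |
|---|---|---|
| 1% | 0 | 0.05 + 0.95 × 0.01 = 5.95% |
| 2% | 0 | 6.9% |
| 5% | 0 | 9.75% |
| 0 | 10% | 0.05 × 0.90 = 4.5% |
| 0 | 25% | 3.75% |
| 0 | 50% | 2.5% |
| 2% | 25% | 0.0375 + 0.019 = 5.65% |

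A shift of 2.1 points is 0.021 × 400 = 8.4 patients net. With 380 truly on-label and 20 truly off-label patients, that is 8.4/380 = 2.2% of the former or 8.4/20 = 42% of the latter. Calling on-label patients off-label is the more sensitive direction. The last row shows that the two errors can partly cancel.

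**4. What can be recovered from the listed data**

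- *Other-class error:* treatment type is an open list, so these patients can be reclassified at analysis.
- *Comma:* it can be settled in the analysis derivation.
- *Refractoriness:* Section 8.3.2 lists platelet counts at the primary condition, at REVOLADE initiation and at dose changes. A low count at initiation despite earlier treatment is a proxy, but it does not document failure of a given treatment.

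**The case against.** Much of the case on the other side stands.

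- **The SAP can repair part of this.** Section 8.7.3 has it finalised before database lock, and it could state the operator and widen the class list. It cannot supply a response item that the eCRF does not collect.
- **For non-splenectomised patients the rule is nearly right.** The label says second line, and receipt of earlier treatment fits that reasonably well.
- **The formal objectives are less exposed.** Section 7 asks for utilisation by condition and age, and for patient characteristics. The patient categories in Section 8.7.1 do not use the prior-treatment test. The labelling aim of Section 8.2.4 and the sizing quantity of Section 8.5.1 do depend on it.

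Three stronger readings are tempting, and the documents do not support them.

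- *That the comma alone swings the off-label proportion by tens of points.* Suppose 90% had corticosteroids and 50% immunoglobulins, independently. The test is then met by 0.9 × 0.5 = 45% under 'and' and by 1 − 0.1 × 0.5 = 95% under 'or'. But these inputs are not in the Protocol, and the figures are the pass rate of one component. Patients must also meet the surgical condition. If a share q does so, independently of prior treatment, the swing is 50 × q points (15 at q = 0.3, 30 at q = 0.6), and q is not given either. The 'and' reading also sits badly with a plan built on 2% to 5% off-label use, so 'or' is probably meant.
- *That the proportion is shown to be wrong, or wrong in a known direction.* Neither the number of patients affected nor the net sign can be derived.
- *That almost every patient will have ITP.* Section 8.2.5 says only that HCV patients will be very few. Sections 8.3.2 and 8.7.1 provide for malignancy, marrow failure and other uses.

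**Conclusion.** The mismatch is real. Sections 8.1 and 8.3.4 state different prior-treatment conditions for the same label, and Section 8.3.2 does not list the variable needed to apply the first ITP arm. The off-label proportion is therefore open to misclassification in both directions: downward through non-refractory splenectomised patients, upward through patients treated earlier only with another class.

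The size is not known. What can be said, taking the plan's own 5% and 400 patients, is that a net 8 to 9 misclassified patients would equal the whole stated half-width. The other-class error and the comma can be corrected after data collection. Refractoriness can then only be approximated, which is the reason to act before abstraction starts. The point concerns how use is classified and implies nothing about how patients should be treated.

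**What to change.** Reconcile the ITP bullets of Section 8.3.4 with the label text in Section 8.1, using two arms, and word the off-label bullet to match.

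- **Not splenectomised, surgery contraindicated:** require at least one documented prior ITP treatment of any class.
- **Splenectomised:** require prior treatment of any class, and record refractoriness in one added eCRF item (refractory / not refractory / not documented). Count patients recorded as not refractory as off-label.
- **Not documented:** report these splenectomised patients as a separate class. Give the off-label proportion with the class counted as on-label and, as a sensitivity analysis, as off-label. With u such patients among 400, the two figures differ by u/400, so 9 patients open a gap of 2.25 points.

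The any-class wording removes both the closed list and the question of the comma.

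The cost is a rewording of Section 8.3.4, one more field to abstract, and some entries of not documented. If charts seldom record response, the gap between the two proportions will be wide, but that uncertainty will then be visible. Adding the field after abstraction has begun would mean going back to charts at 18 to 21 sites.

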7. RESEARCH QUESTION AND OBJECTIVES

The aim of this DUS is to determine indications for use among REVOLADE users within several EU countries utilizing real-world data obtained in medical records.

The objectives of the study are:

- To document REVOLADE utilisation patterns, classified according to the medical conditions and the patient age categories for which REVOLADE is being prescribed in selected European countries
- To characterize the patients who are prescribed REVOLADE in routine clinical practice.

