8.6.3. File Retention and Archiving

To enable audits from regulatory authorities or GSK, the investigator must agree to keep records, including the identity of all participating patients, all original signed informed consent forms (ICFs), patient screening logs, copies of all eCRFs (which will be provided by sponsor at study end), source documents and adequate documentation of relevant correspondence. The records should be retained by the investigator. The records must be available for review in the event the site is selected for monitoring, audits, or inspections and must be safely archived following the study conclusion, according to local regulations or as specified in the contract, whichever is longer. In the event that archiving of the file is no longer possible at the site, the site will be instructed to notify GSK.

8.7. **Data Analysis**

8.7.1. **DUS Analyses**

This is a multinational, retrospective, observational, medical chart review study. A Statistical Analysis Plan (SAP) describing the detailed statistical methodology and analysis will be provided as a separate document.

Continuous variables will be reported as mean, standard deviation, median and range. Categorical variables will be summarised as number and proportion of the total study population (counting missing data as a class), and by subgroups if and where appropriate. Confidence intervals (as 95% CI) will be calculated using the method outlined by Newcombe (Newcombe, 1998) for the key variables.

Participating physicians

Number of participating physician, and practice setting, will be summarized descriptively.

Page 126

Patient demographics and disease characteristics

Descriptive statistics will be given for the variables below:

- Age at time of initial REVOLADE prescribing dose
- Gender
- Race/Ethnicity
- Relevant medical history for applicable conditions

REVOLADE Patient characteristics

Number and percentage of the following categories will be described and stratified if number permits according to the dates of new indication approval:

- Adult chronic ITP patients
- Adult patients with HCV and clinically meaningful thrombocytopenia
- Patients < 18 years with chronic ITP
- Patients < 18 years with HCV (with and without thrombocytopenia)
- Patients < 18 years without chronic ITP or HCV but with another disease type, by specific disease type
- Adult patients with cancer, by cancer type
- Adult patients with myelodysplastic syndrome/AML

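### Section 8.3.4 assigns label status from the diagnoses a patient carries, not from the recorded indication, so an adult with both chronic ITP and HCV can be on-label and off-label at once

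*Protocol*

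**What the plan says.** Section 7 of the protocol sets the purpose: "The aim of this DUS is to determine indications for use among REVOLADE users". Section 8.3.3 accordingly lists "Indication for REVOLADE" as a variable of its own.

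Section 8.3.4 defines label status. Where splenectomy, prior medication and contraindications are documented, "then use of eltrombopag for a patient will be categorized into the following groups". The lines that matter here are:

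- On-label, ITP: "patient is an adult, has a diagnosis of chronic ITP, has been splenectomized or has a contraindication for surgery, and has received prior corticosteroids" or immunoglobulin therapy.
- On-label, HCV, joined to the ITP line by *or*: "has a diagnosis of chronic HCV, has clinically meaningful thrombocytopenia limiting interferon-based therapy, and date of eltrombopag is after REVOLADE approval date" (September 2013).
- Off-label, ITP: "patient is an adult, has chronic ITP, but has not received prior corticosteroids, immunoglobulins therapy or has not been splenectomized" and has no contraindication for surgery.
- Off-label, HCV: an adult with HCV who lacks interferon-limiting thrombocytopenia, or whose REVOLADE date precedes approval.
- Off-label, other: an adult with neither ITP nor HCV.
- Off-label, age: anyone under 18.

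A coarser set of lines applies when the splenectomy, medication and contraindication data are absent. It too is built on the diagnoses held.

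**The concern.** No line in 8.3.4 asks what REVOLADE was prescribed for, and nothing says which line prevails when two apply. Two kinds of error follow.

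1. **Contradictory class.** A patient with both labelled diseases can satisfy an on-label line through one disease and an off-label line through the other.
2. **Single but wrong class.** Use for a third disease is off-label only if the adult has neither ITP nor HCV. A splenectomised, pretreated adult with chronic ITP who received the drug for, say, a haematological malignancy is counted on-label.

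The off-label proportion is the only quantity for which section 8.5.1 gives a precision. Section 8.2.4 also says the data will be used to judge whether prescribing follows the label. Two analysts who follow 8.3.4 to the letter could report different proportions from the same charts.

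**Working it through.** **The plan's own figure.** Inputs from section 8.5.1: p = 0.05, n = 400. Half-width = 1.96 × √(0.05 × 0.95 / 400) = 0.0214, so 2.9% to 7.1%. This agrees with the protocol.

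**Conditions in the main set of lines.** Take an adult with both chronic ITP and HCV. Five yes/no facts decide the class: splenectomy, contraindication for surgery, prior therapy, interferon-limiting thrombocytopenia, and date after approval. That gives 2⁵ = 32 combinations. (ITP is taken as chronic or absent, and prior corticosteroid or immunoglobulin therapy as one fact.)

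- ITP on-label needs (splenectomy or contraindication) and prior therapy: 3 of 4 times 1 of 2, or 3 of 8. The ITP off-label line is the complement, 5 of 8.
- HCV on-label needs limiting thrombocytopenia and a date after approval: 1 of 4. The HCV off-label line is the complement, 3 of 4.

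| | HCV on-label (1) | HCV off-label (3) |
|---|---|---|
| ITP on-label (3) | 3 × 1 = 3, on-label only | 3 × 3 = 9, **both** |
| ITP off-label (5) | 5 × 1 = 5, **both** | 5 × 3 = 15, off-label only |

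Both classes: 9 + 5 = 14 of 32. With chronic ITP alone, HCV alone or neither, there are 3 × 32 = 96 combinations and none is double. The conflict in this set therefore comes only from ITP together with HCV.

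**Two examples.**

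- Splenectomised, pretreated chronic ITP, coincident HCV, REVOLADE started before September 2013: on-label through ITP, off-label through the HCV date clause, even if the drug was given for ITP.
- Chronic ITP without splenectomy or contraindication, plus HCV with interferon-limiting thrombocytopenia, treated after September 2013: off-label through ITP, on-label through HCV.

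**Reach of the date clause.** Eligibility (section 8.2.5) opens in April 2010 in Germany, December 2010 in Spain and January 2011 in France, and ends in September 2014. The months before September 2013 are 41 of 53, 33 of 45 and 32 of 44, which is 77%, 73% and 73% of the windows. For most of each window, any coincident HCV triggers the off-label HCV line.

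**Coarser set of lines.** Acute ITP plus qualifying HCV after approval is both on-label and off-label. Chronic ITP plus qualifying HCV before approval is both under one of the two possible readings of the second off-label line.

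**The single wrong class.** Section 6.2 describes ITP secondary to leukaemia and lymphoma. Section 8.3.2 collects haematological malignancies, aplastic anaemia and other diagnoses beside ITP and HCV. Coexistence is thus foreseen. An adult who meets the ITP on-label line and was treated for one of these other diseases is on-label by 8.3.4, so this error lowers the off-label count.

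**Sensitivity of the estimate.** Expected off-label patients at n = 400: 2% × 400 = 8 to 5% × 400 = 20. One reclassified patient moves the proportion by 1/400 = 0.25 points (0.33 at n = 300, 0.22 at n = 450). It would take nine patients, all moved the same way, to exceed the 2.1-point half-width (9/400 = 2.25). That is a threshold, not a forecast.

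**The case against.** The protocol's intent is fairly clear. It lists a primary diagnosis in the singular, refers to a primary medical condition, frames its first objective around the conditions for which the drug is prescribed, and in 8.3.4 categorises use rather than a diagnosis list. A sensible analyst could read each line as referring to the condition treated, and a tie-break could go into the SAP, which section 8.7.3 requires before database lock. This shows intent but supplies no precedence rule. The protocol fixes the definition itself, and its literal text conflicts.

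It is also fair that the conflict may be rare. Section 8.2.5 expects very few patients with HCV-associated thrombocytopenia, which limits the second example. It does not bound coincident HCV among ITP patients, so the first example has no documented frequency. How often a patient with on-label ITP is treated for something else is likewise unknown.

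A reader might go further in four ways that the documents do not support:

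- **Any second diagnosis creates ambiguity.** It does not. In the main set a double label needs ITP plus HCV; ITP with cancer gives one class, possibly the wrong one.
- **The bias can be put at some number of percentage points.** No share of patients with two diagnoses is given, and reclassifications may partly cancel.
- **The study would report comorbid diagnoses instead of indications.** Indication is collected, and section 8.7.1 tabulates platelet counts by indication.
- **The overlapping patient categories in 8.7.1 are an error.** That list is descriptive and nowhere claims to be mutually exclusive.

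**Conclusion.** Wrong as written. Followed literally, section 8.3.4 can give two opposite classes to an adult with both chronic ITP and HCV (14 of 32 rule combinations) and can count use for an unlabelled disease as on-label when the patient also meets the ITP on-label line. The first error has no fixed direction; the second understates off-label use.

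The logical result rests only on the text of 8.3.4. The number of patients affected cannot be derived from the protocol, so the supported statement is that patients can be misclassified, not that a known share will be. It matters because the planning range implies only 8 to 20 off-label patients in 400.

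**What to change.** In section 8.3.4, make the indication recorded under 8.3.3 the governing variable:

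- Apply the ITP lines only when the recorded indication is ITP, and the HCV lines only when it is HCV-associated thrombocytopenia.
- Count any other recorded indication as off-label.
- Where no indication is recorded, use the diagnosis-based lines only if they yield a single class. Otherwise report the patient as unclassifiable in a separate row, and give the off-label proportion with those patients counted first all as on-label and then all as off-label.

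The last step is needed because an unrestricted return to the diagnosis-based lines would restore the same ITP-HCV conflict. As 8.2.3 captures repeated treatment intervals, the wording should also say which interval's indication governs if it changes.

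No new data are required. The cost is a wording change in the protocol, the matching derivation in the SAP, and one table row with its two bounding proportions.

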8.7.2. Handling of Missing Data

In general, missing data will not be imputed and will be analyzed as they are recorded in the study CRF.

Page 127 WEUKBRE7133

The proportion of missing data will be reported for each measured variable in the study.

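### When label criteria are undocumented, Section 8.3.4 counts an adult with chronic ITP as on-label by diagnosis alone; in this group missing chart information can only lower the off-label proportion

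*Protocol*

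**What the plan says.** Section 8.3.4 of the Protocol applies its full definition under a condition: "If information on splenectomy, prior medication use, and contraindications for surgery is available". An adult with chronic ITP is then on-label only if the patient "has been splenectomized or has a contraindication for surgery, and has received prior corticosteroids, immunoglobulins therapy". The matching off-label entry begins "patient is an adult, has chronic ITP, but has not received prior corticosteroids, immunoglobulins therapy or has not been splenectomized" and goes on to require that no contraindication to surgery is present.

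The second rule is introduced by "If there is no information on splenectomy, prior medication use, and contraindications for surgery, then classification will be more general". Its whole on-label test for ITP is "patient is an adult and has a diagnosis of chronic ITP". Its only ITP entry under off-label is "patient is an adult, but has acute rather than chronic ITP". Neither rule has a class for patients who cannot be classified.

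Elsewhere the Protocol treats missing data differently. Section 8.7.1 summarises categorical variables "counting missing data as a class". Section 8.7.2 says "In general, missing data will not be imputed and will be analyzed as they are recorded in the study CRF", and also asks for the proportion missing on each variable.

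Section 8.5.1 sizes the study on the precision of the off-label proportion. Section 8.2.4 says the data will be used to see whether prescribing follows the labelling.

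**The concern.** The same patient can receive opposite classes depending on what the chart holds. Take an adult with chronic ITP who in truth fails the label criteria. If the chart shows this, the patient is off-label; if it is silent on all three items, the patient is on-label. Absent information is handled as though the criteria were met.

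Chronic ITP is where this matters most. Section 8.2.5 expects very few HCV patients, so chronic ITP is the dominant approved use in the sample. The fallback keeps the thrombocytopenia and approval-date conditions for HCV, so the loosening falls on ITP.

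Two gaps add to this. The branch conditions do not cover a chart with some of the three items but not all. Adult acute ITP is named as off-label in the fallback but appears in neither list of the full-information rule. At stake is a one-way error in the quantity that justifies the study size.

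**Working it through.** **1. The plan's own figure.** Section 8.5.1 gives a precision of 2.1 points for a 5% rate with 400 patients. The simple (Wald) half-width is 1.96 × √(p(1−p)/n) = 1.96 × √(0.05 × 0.95 / 400) = 0.0214, giving 2.9% to 7.1%. This reproduces the stated figure. The Table 1 column labelled as CI width holds half-widths.

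**2. The two branches side by side, for adults.**

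| Patient | Full-information rule | Fallback rule |
|---|---|---|
| Chronic ITP, criteria met | on-label | on-label |
| Chronic ITP, criteria not met | off-label | on-label |
| Acute ITP | not listed | off-label |
| Some of the three items known, others missing | condition not met | condition not met, read literally |

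In the two chronic ITP rows the only change between columns is from off-label to on-label. The direction follows from the wording and needs no assumption.

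**3. Size.** Let p be the true off-label proportion, s the share of off-label patients who are adults with chronic ITP, and m the share of those who reach the fallback. The expected estimate is p × (1 − s × m), so the shift is −p × s × m. The Protocol uses 5% as a planning value for p. It gives neither s nor m, so both are assumptions.

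With p = 5% and s = 0.8:

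| m | Expected estimate | Shift (points) |
|---|---|---|
| 0.1 | 5 × (1 − 0.08) = 4.6% | −0.4 |
| 0.2 | 5 × (1 − 0.16) = 4.2% | −0.8 |
| 0.3 | 5 × (1 − 0.24) = 3.8% | −1.2 |
| 0.5 | 5 × (1 − 0.40) = 3.0% | −2.0 |

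In counts for m = 0.5: 400 × 0.05 = 20 off-label patients, of whom 16 are adults with chronic ITP. Eight of these are relabelled, leaving 12/400 = 3.0%.

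Over the same range of m, the shift is −0.25 to −1.25 points with s = 0.5, and −0.5 to −2.5 points with s = 1.0.

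**4. Effect on the interval.** Around 3.0% with n = 400, the Wald upper limit is 3.0 + 1.67 = 4.7%, below the true 5%. The Wilson score upper limit is 5.2%, which just includes it. For m of 0.3 or less (s = 0.8), the Wald interval around the expected estimate still includes 5%. The shift contains no n, so enlarging the sample narrows the interval around the wrong value.

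**5. If true off-label use is higher.** With p = 20% and s = 0.8, the expected estimates for the same four values of m are 18.4%, 16.8%, 15.2% and 12.0%, a shift of −1.6 to −8.0 points. The relative loss, s × m, is the same 8% to 40% as before.

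**The case against.** The case for leaving the text alone has several parts.

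- **The trigger is narrow.** The fallback condition joins the three items with 'and'. A reader might infer that one missing item sends a patient to the looser rule. The text does not say so: read literally, all three must be missing. Partial charts are therefore an undefined case, not a demonstrated bias. This stands, and it makes m smaller on the literal reading.
- **Section 8.7.2 is a general rule.** It opens with a qualifier, and the fallback fills in no splenectomy or treatment value; it applies a coarser definition. A flat contradiction is not supported. The departure is one of effect, and no exception is declared.
- **Missingness will be visible.** The proportion missing is to be reported per variable. That helps a reader, but the patients remain labelled on-label.
- **Pooling is not stated.** The Protocol does not say that the two tiers are merged into one figure, and an SAP could report them apart. So a reader should not conclude that the result cannot be interpreted. But an SAP that follows Section 8.3.4 would still call these patients on-label.
- **Frequency is undocumented.** Section 8.3.2 plans to collect splenectomy status, comorbidities that may contraindicate surgery, and preceding treatments for all patients. Nothing shows how often charts omit them, or that countries with poorer charts would look more compliant. Both are possibilities only.
- **Large distortions need large true rates.** A reader might multiply a 90% chronic ITP share by 30% lacking information and 40% off-label to get 10.8 points. That presupposes off-label use of 0.9 × 0.4 = 36% of the sample and cannot be set against a 5% planning rate. At 5%, the shift cannot exceed 5 points.

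These points limit the size and reach of the concern. They do not change the direction of error for adults with chronic ITP.

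**Conclusion.** The concern holds in a limited form. For adults with chronic ITP, the fallback in Section 8.3.4 can only move patients from off-label to on-label. It is fixed in the Protocol, not left to the SAP. The one-way claim does not extend to charts with partial information or to adult acute ITP, where the fault is an incomplete rule.

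The size is not known. At the 5% planning rate, with the assumed s = 0.8 and m = 0.1 to 0.5, the loss is 0.4 to 2.0 points. Every value in that range is below the planned half-width of 2.1, but the top nearly equals it. The loss is zero only if no off-label adult with chronic ITP reaches the fallback. The rule should be changed before patients are classified.

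**What to change.** Reword Section 8.3.4, and carry the change into the SAP derivation, as follows.

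1. Apply the full-information definition to every patient, with three classes: on-label, off-label and not determinable. Use the third only when a criterion that decides the class is missing. For example, under the Protocol's own definition, a splenectomised adult with chronic ITP and documented prior therapy is classifiable even if contraindications are unrecorded.
2. List adult acute ITP consistently in both branches.
3. State how a chart with no contraindication recorded is coded. Section 8.3.2 collects comorbidities that may contraindicate surgery but lists no yes/no/unknown judgement.
4. Report the off-label proportion among determinable patients, the not-determinable share, and two bounds: that class counted all on-label, then all off-label.
5. Keep the more general rule, if at all, as a separately reported sensitivity analysis.

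This uses data already planned, so the cost is rewording. The downside is a visible not-determinable class and a wider range for the headline figure.
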